5.4 DURATION OF THERAPY

In the absence of treatment delays due to adverse event(s), treatment may continue without a limitation on the number of cycles, unless one of the following criteria applies:

- ❖ Disease progression after two cycles or later of therapy
- ❖ Intercurrent illness that prevents further administration of treatment
- ❖ Unacceptable adverse event(s)
- ❖ Patient decides to withdraw from the study
- ❖ General or specific changes in the patient's condition render the patient unacceptable for further treatment in the judgment of the investigator
- ❖ Patient becomes pregnant
- ❖ Patient loses the ability to freely provide consent through imprisonment or involuntary incarceration for treatment of a psychiatric or physical illness
- ❖ Patient achieves complete remission (CR), and the patient and investigator feel that discontinuation of cabozantinib is in the patient's best interests, or
- ❖ Patient achieves a level of response that qualifies him or her for another therapy for which they provide consent, such as high dose therapy with autologous stem cell transplantation.

5.5 DURATION OF FOLLOW-UP

Patients will be followed for 30 days after removal from study or until death, whichever occurs first. Patients removed from study for unacceptable adverse event(s) will be followed until resolution or stabilization of the adverse event.

5.6 CRITERIA FOR REMOVAL FROM STUDY

Patients will be removed from study when any of the criteria listed in Section 5.4 applies. The reason for study removal and the date the patient was removed must be documented in the Case Report Form.

5.7. DOSING DELAYS / DOSE MODIFICATIONS

In Phase I of this study we will determine the MTD among three doses. DLTs will be based solely on adverse events that occur during cycle 1. The definition of DLT includes:

- a. Any non-hematological toxicity Grade ≥ 3 , except for alopecia and nausea uncontrolled by medical management.
- b. Grade 4 neutropenia lasting more than 5 days.
- c. Febrile neutropenia of any duration (ANC $<1.0 \times 10^9/L$ fever $\geq 38.5^{\circ}\text{C}$)
- d. Grade 4 thrombocytopenia, or Grade 3 thrombocytopenia with bleeding, or any requirement for platelet transfusion
- e. Grade 4 anemia, unexplained by underlying disease.

We will study three dose levels using the 3+3 algorithm, so that we will accrue a minimum of 3 patients and a maximum of 18 patients in Phase I. The initial dose of cabozantinib for all patients treated on this study will be 20 mg P.O. daily, which is designated dose level -1. In the event that dose modifications are needed for toxicities, the following additional dose levels will be used:

Dose Level	Cabozantinib Dose
-1	20 mg p.o., daily
0	40 mg p.o., daily
+1	60 mg p.o., daily

To allow for optimal experimental design, capped dose of carfilzomib of 27 mg/m^2 will be used in the study without dose escalations or de-escalations. Given the potential for compounding/worsening toxicities with the addition of cabozantinib to carfilzomib, patients eligible for the trial will have to have had very good tolerance to carfilzomib in the context of treatment regimens they were receiving, with resolved prior carfilzomib toxicities to grade 1 or better, and no toxicities due to carfilzomib that required dose reductions to less than 27 mg/m^2 as dose adjustments will be allowed in the cabozantinib only. Stopping of carfilzomib however will be allowed if the adverse events secondary to carfilzomib that require its stopping are observed/met.

Specific dose modifications guidelines will be followed for the adverse events nausea, vomiting, diarrhea, neutropenia, and thrombocytopenia, and are detailed below. If a patient experiences several adverse events and there are conflicting recommendations, the investigator should use the recommended dose adjustment that reduces the dose to the lowest level.

Event Name	Diarrhea
Grade of Event	Management/Next Dose for Cabozantinib
\leq Grade 1	No change in dose
Grade 2	Hold until \leq Grade 1. Resume at same dose level.
Grade 3	Hold* until $<$ Grade 2. Resume at one dose level lower, if indicated.**
Grade 4	Off protocol therapy

^{*}Patients requiring a delay of >2 weeks should go off protocol therapy.

^{**}Patients requiring > two dose reductions should go off protocol therapy.

Recommended management: Loperamide anti-diarrheal therapy

Dosage schedule: 4 mg at first onset, followed by 2 mg with each loose motion until diarrhea-free for 12 hours (maximum dosage: 16 mg/24 hours).

Adjunct anti-diarrheal therapy is permitted and should be recorded when used.

Event Name	Vomiting
Grade of Event	Management/Next Dose for Cabozantinib
≤Grade 1	No change in dose
Grade 2	Hold until ≤Grade 1. Resume at same dose level.
Grade 3	Hold* until <Grade 2. Resume at one dose level lower, if indicated.**
Grade 4	Off protocol therapy

^{*}Patients requiring a delay of >2 weeks should go off protocol therapy.

^{**}Patients requiring > one dose reductions should go off protocol therapy.

Recommended management: Antiemetics.

Event Name	Nausea
Grade of Event	Management/Next Dose for Cabozantinib
≤Grade 1	No change in dose
Grade 2	Hold until ≤Grade 1. Resume at same dose level.
Grade 3	Hold* until <Grade 2. Resume at one dose level lower, if indicated.**
Grade 4	Off protocol therapy

^{*}Patients requiring a delay of >2 weeks should go off protocol therapy.

^{**}Patients requiring > one dose reductions should go off protocol therapy.

Recommended management: Antiemetics.

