During treatment with cabozantinib good oral hygiene and standard local treatments such as nontraumatic cleansing and oral rinses (eg, with a weak solution of salt and baking soda) should be maintained. The oral cavity should be rinsed after meals, and dentures should be cleaned and brushed often to remove plaque. Local treatment should be instituted at the earliest onset of symptoms. Obtain bacterial/viral culture if oral infection is suspected and treat infection as indicated by local guidelines. When stomatitis interferes with adequate nutrition and local therapy is not adequately effective, dose reduction or temporary withholding of cabozantinib should be considered per the table For other non-hematologic adverse events, and for hematologic adverse events, the following criteria for dose reduction should be used:

Table 5-1: Recommended carfilzomib and cabozantinib dose modification plan for hematologic and non-hematologic toxicities.

Event Grade (NCI CTC V4.03) and Category		Action by Agent	
Grade	Adverse Event	Carfilzomib	Cabozantinib
Grade 2	Pulmonary Hypertension or Pulmonary Complications	Withhold carfilzomib until resolved or returned to baseline. Restart at the dose used prior to the event or reduced dose (from 27 mg/m ² to 20 mg/m ² , OR from 20 mg/m ² to 15 mg/m ²), at the discretion of the physician. If tolerated, the reduced dose may be escalated to the previous dose at the discretion of the physician.	
	Congestive heart failure or myocardial ischemia	Withhold carfilzomib until resolved or returned to baseline. Restart at the dose used prior to the event or reduced dose (from 27 mg/m ² to 20 mg/m ² , OR from 20 mg/m ² to 15 mg/m ²), at the discretion of the physician. If tolerated, the reduced dose may be escalated to the previous dose at the discretion of the physician.	
	Rash, or hand-foot syndrome only		Withhold cabozantinib until recovery to Grade 1 or screening value. Administer cabozantinib at the next lower dose for subsequent cycles, unless further dose reduction is required. If a second hold is required for the same event, administer cabozantinib at lower dose for subsequent cycles.

Event Grade (NCI CTC V4.03) and Category		Action by Agent	
Grade	Adverse Event	Carfilzomib	Cabozantinib
	Non-hematologic toxicities		Continue current dose level.

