Grade 3	Hematologic (neutropenia, thrombocytopenia, anemia)	
Withhold carfilzomib dose.
 
If fully recovered before next scheduled dose, continue at same dose level.
 
If recovered to Grade 2 neutropenia or Grade 3 thrombocytopenia, reduce dose by one dose level: from 27 mg/m² to 20 mg/m², OR from 20 mg/m² to 15 mg/m².
 
If tolerated, the reduced dose may be escalated to the previous dose at the discretion of the physician.
 
TMA: If TMA is suspected, hold carfilzomib and manage per standard of care. If TMA is confirmed and related to carfilzomib, permanently discontinue carfilzomib. If TMA is excluded, may restart carfilzomib.
	
Withhold cabozantinib.
 
If the relevant lab value recovers to: $1.0 \times 10^9/L$ for ANC, 8 g/dL for hemoglobin, or $50 \times 10^9/L$ for platelets, resume cabozantinib treatment at same dose level. If the relevant lab value takes more than 3 weeks to recover to the level described above, restart cabozantinib administration at the next lower dose. If a second hold is required for the same event, administer cabozantinib at the next lower dose for subsequent cycles (for those subjects starting at 40 mg dose, cabozantinib would be discontinued if second hold required).

	Hepatic Toxicity	
25% dose reduction in case of baseline or treatment emergent mild or moderate hepatic impairment. Withhold carfilzomib until resolved or returned to baseline. After resolution, consider if restarting is appropriate. May be restarted at the dose (from 27 mg/m² to 20 mg/m², OR from 20 mg/m² to 15 mg/m²) with frequent monitoring of liver function. If tolerated, the reduced dose may be escalated to the previous dose at the discretion of the physician. Monitor liver enzymes regularly, regardless of baseline values, and modify dose based on toxicity.
	

Event Grade (NCI CTC V4.03) and Category		Action by Agent	
Grade	Adverse Event	Carfilzomib	Cabozantinib
	Renal	Serum creatinine ≥ 2 times baseline, CrCl < 15 mL/minute or CrCl decreases to $\leq 50\%$ of baseline, or patient requires dialysis: Withhold dose and monitor renal function. If renal toxicity is due to carfilzomib, resume dosing when renal function has improved to within 25% of baseline; resume with a reduced dose by 1 dose level.	

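### Section 5.7 confines dose adjustment to cabozantinib, yet Table 5-1 in the same section lowers carfilzomib in ten rows, and no text says which governs

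*Combined protocol and SAP*

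**What the plan says.** The body text of Section 5.7 makes three statements about carfilzomib:

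- The capped dose of 27 mg/m² "will be used in the study without dose escalations or de-escalations".
- Patients who needed a reduction below 27 mg/m² for carfilzomib toxicity are not eligible, "as dose adjustments will be allowed in the cabozantinib only".
- One exception is then made for this drug: "Stopping of carfilzomib however will be allowed if the adverse events secondary to carfilzomib that require its stopping are observed/met".

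It then promises event-specific rules: "Specific dose modifications guidelines will be followed for the adverse events nausea, vomiting, diarrhea, neutropenia, and thrombocytopenia, and are detailed below". The three tables that follow immediately (diarrhea, vomiting, nausea) have a single action column, "Management/Next Dose for Cabozantinib".

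Table 5-1 comes later, in Section 5.7.1. Its title calls it a recommended modification plan for both drugs. Its lead-in is firmer: "For other non-hematologic adverse events, and for hematologic adverse events, the following criteria for dose reduction should be used". The carfilzomib column gives steps from 27 to 20 and from 20 to 15 mg/m².

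Section 8.2.4 describes 27 mg/m² as a maximum capped starting dose and says nothing about later reductions.

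**The concern.** The body text and the table give different instructions for the same patient. When the condition in a directive row is met, the table calls for a lower carfilzomib dose and the body text does not allow one. An investigator cannot comply with both.

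Three things are at stake:

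- **Patient safety.** With two sites (Section 10.3), the same toxicity could be followed by different carfilzomib doses.
- **The MTD.** It is defined for cabozantinib added to carfilzomib (Section 1.1), so the carfilzomib dose actually given is part of what is being declared tolerable.
- **The ORR.** Responses would be observed on a carfilzomib dose that depends on which text a site followed.

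**Working it through.** **1. Does the body text really restrict individual patients?** Taken alone, the first statement could be a rule for dose cohorts: it follows the dose-level table and explains the experimental design. The other two cannot be read that way. Confining adjustment to cabozantinib is given as the reason for an eligibility requirement on individual tolerance, and the stopping exception is triggered by an adverse event in a patient.

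**2. What does Table 5-1 do with carfilzomib?** Row by row:

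| Row | Carfilzomib reduction | Type | Return to previous dose allowed |
|---|---|---|---|
| Grade 2 pulmonary | prior or reduced dose, physician's choice | permits | yes |
| Grade 2 heart failure or ischemia | prior or reduced dose, physician's choice | permits | yes |
| Grade 3 hematologic | one level, after partial recovery | directs | yes |
| Hepatic | 25% for mild or moderate impairment; restart wording is permissive | directs (25% clause) | yes |
| Renal | one level, if due to carfilzomib | directs | no |
| Grade 3 or 4 cardiac | to be considered | permits | yes |
| Peripheral neuropathy | to be considered | permits | yes |
| Grade 3 other non-hematologic | to be considered | permits | yes |
| Grade 4 non-hematologic | to be considered | permits | yes |
| Grade 4 hematologic | one level, after partial recovery | directs | yes |

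Totals: 4 direct + 6 permit = 10 rows; 9 allow re-escalation. The remaining rows contain no carfilzomib reduction (cabozantinib action only, interruption, or discontinuation).

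The hematologic rows are conditional. In the Grade 3 row, for example: "If fully recovered before next scheduled dose, continue at same dose level". Only partial recovery triggers the reduction. In that row cabozantinib resumes at the same level unless laboratory recovery takes more than 3 weeks or a second hold is needed. The table can therefore lower carfilzomib and leave cabozantinib unchanged, the reverse of the body text.

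**3. Does the body text point away from the table?** No. It says that neutropenia and thrombocytopenia guidelines will be followed and appear below. The symptom tables do not contain them; they appear only in Table 5-1. Section 5.7 thus sends the reader to the text that it contradicts.

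**4. Does anything set precedence?**

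- "If a patient experiences several adverse events and there are conflicting recommendations, the investigator should use the recommended dose adjustment" that gives the lowest dose. This covers one patient with several events; it does not rank text against table.
- The lead-in to Table 5-1 introduces the criteria without mentioning or lifting the restriction.
- Section 8.1.4 refers dose changes back to Section 5.7, which is circular.
- Section 8.2.4's starting-dose wording is compatible with later reductions but does not authorise them.

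**5. Size of one step.** Carfilzomib is given on days 1, 2, 8, 9, 15 and 16, so 6 doses per cycle. Assuming all six are at the same level:

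- Relative reduction: 1 − 20/27 = 0.259, about 26%.
- Per cycle: 6 × 27 = 162 mg/m²; 6 × 20 = 120 mg/m²; difference 42 mg/m².
- Two steps, to 15 mg/m²: 1 − 15/27 = 0.444, about 44%; 6 × 15 = 90 mg/m² per cycle.
- Hepatic cell: a 25% reduction gives 0.75 × 27 = 20.25 mg/m², against 20 mg/m² by the step rule. (20.25 − 20)/20.25 = 0.012, about 1%. The problem there is which wording applies, not the size.

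**6. Reach into the primary results.** For the MTD, the relevant events are those in cycle 1 that lead to a carfilzomib reduction without counting as a DLT. Grade 3 neutropenia without fever is an example: neither Section 5.7 nor Section 10.1 lists it as a DLT, yet the table can direct a reduction. The set also depends on which DLT definition applies. Grade 4 neutropenia of 5 days or less without fever is not a DLT under Section 5.7, but may be one under Section 10.1 if the hold in Table 5-1 delays treatment and the event is judged treatment-related and unmanageable. For the ORR, the analysis set does not change: Section 10.7.2 keeps patients in despite treatment deviations.

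**The case against.** The best defence is that the documents are not silent. The body text says that the neutropenia and thrombocytopenia rules will be followed, and the table's lead-in says that its criteria should be used. A capped or maximum starting dose describes an upper limit. All this suggests that the table was meant to operate, and that the restriction was about dose finding. It is fair evidence of intent, but it does not remove the clause confining adjustment to cabozantinib, and a site that follows that clause literally is also following the protocol.

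Other points have some force:

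- **The 4 and 6 split involves a judgement.** The hepatic cell mixes a 25% clause with permissive restart wording; classed by the latter, the split is 3 and 7. The baseline part of that clause is also narrowed, because known moderate or severe hepatic impairment is an exclusion (Section 3.2). The total of ten rows is unaffected.
- **Stopping is allowed under either reading.** The body text does not force dosing through an event that requires stopping. The disagreement is about the dose on resumption, which limits the safety concern but does not remove it.
- **The consequences shown are bounded.** Six rows are discretionary, the MTD route is limited to cycle 1 events that are not DLTs, and the ORR set is fixed.
- **Evaluability for toxicity in Section 10.7.1 is not a definition of DLT evaluability.** That is true. However, Section 10.2 bases the 3+3 decision on DLTs, and nothing in the plan removes a patient whose carfilzomib was reduced.

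**Conclusion.** The contradiction is real and must be fixed. Section 5.7 allows adjustment of cabozantinib only, with stopping as the sole carfilzomib exception. Table 5-1 contains a carfilzomib reduction in ten rows: four directive under a condition (counting the hepatic 25% clause as directive), six permissive, and nine with re-escalation. No text says which governs.

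Where a directive condition is met, the two texts differ by one step, about 26% of the carfilzomib dose, or 42 mg/m² per cycle if all six doses are affected. The number of patients concerned is unknown. The effect on the MTD is limited and the ORR denominator is unchanged, but the carfilzomib dose behind both results is not determined by the plan as written. This conclusion takes no position on which carfilzomib rule is clinically right.

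**What to change.** Reconcile three places so that one carfilzomib rule, chosen by the sponsor, applies at both sites:

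- the body text of Section 5.7, including the neutropenia and thrombocytopenia guidelines that it promises;
- the carfilzomib column of Table 5-1, including the two figures in the hepatic cell;
- Section 8.2.4.

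If carfilzomib reductions are kept, summarise carfilzomib dose intensity alongside the MTD and ORR. Section 11.1 already requires dated records of doses given and reasons for changes, so no new data are needed. No separate counting rule is needed either: 3+3 decisions rest on DLTs (Section 10.2), and all patients are evaluable for toxicity from their first cabozantinib treatment (Section 10.7.1).

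The cost is a protocol wording amendment, with no extra patients or procedures.

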5.7.1 PRECAUTIONS, WARNINGS, AND OTHER SUPPORTIVE CARE GUIDELINES

Gastrointestinal Disorders

The most common non-hepatobiliary GI AEs reported in clinical studies with cabozantinib regardless of causality are diarrhea, nausea, decreased appetite, vomiting, constipation, stomatitis and abdominal pain.

Diarrhea

Subjects should be instructed to notify their physician immediately at the first signs of poorly formed or loose stool or an increased frequency of bowel movements. Administration of antidiarrheal/antimotility agents is recommended at the first sign of diarrhea as initial management. Some subjects may require concomitant treatment with more than one antidiarrheal agent. When therapy with antidiarrheal agents does not control the diarrhea to tolerable levels, study treatment should be temporarily interrupted or dose reduced per above table.

In addition, general supportive measures should be implemented including hydration, correction of fluid and electrolyte abnormalities, small frequent meals, and stopping lactose-containing products, high fat meals, and alcohol.

Nausea and Vomiting

Antiemetic agents are recommended as clinically appropriate at the first sign of nausea and vomiting or as prophylaxis to prevent emesis, along with supportive care in accordance to clinical practice guidelines. The 5-HT3 receptor antagonists are recommended over chronic use of NK-1 receptor antagonists and dexamethasone (NK-1 receptor antagonists can induce or inhibit CYP3A4, and glucocorticoids induce CYP3A4 and thus could lower cabozantinib exposure (see Sections 5.3.5). Caution is also recommended with the use of nabilone, which is a weak inhibitor of CYP3A4. When therapy with antiemetic agents does not control the nausea or vomiting to tolerable levels, study treatment should be temporarily interrupted or dose reduced per the above table.

Dehydration may be associated with vomiting and monitoring for and correction of fluid and electrolyte disturbances should be implemented.

Stomatitis and Mucositis

Preventive measures may include a comprehensive oral examination to identify and treat any potential risk for complications before study treatment is initiated. Appropriate correction of local factors should be instituted as indicated, such as modification of ill-fitting dentures and appropriate care of gingivitis.

During treatment with cabozantinib good oral hygiene and standard local treatments such as nontraumatic cleansing and oral rinses (eg, with a weak solution of salt and baking soda) should be maintained. The oral cavity should be rinsed after meals, and dentures should be cleaned and brushed often to remove plaque. Local treatment should be instituted at the earliest onset of symptoms. Obtain bacterial/viral culture if oral infection is suspected and treat infection as indicated by local guidelines. When stomatitis interferes with adequate nutrition and local therapy is not adequately effective, dose reduction or temporary withholding of cabozantinib should be considered per the table For other non-hematologic adverse events, and for hematologic adverse events, the following criteria for dose reduction should be used:

Table 5-1: Recommended carfilzomib and cabozantinib dose modification plan for hematologic and non-hematologic toxicities.

Event Grade (NCI CTC V4.03) and Category		Action by Agent	
Grade	Adverse Event	Carfilzomib	Cabozantinib
Grade 2	Pulmonary Hypertension or Pulmonary Complications	Withhold carfilzomib until resolved or returned to baseline. Restart at the dose used prior to the event or reduced dose (from 27 mg/m ² to 20 mg/m ² , OR from 20 mg/m ² to 15 mg/m ²), at the discretion of the physician. If tolerated, the reduced dose may be escalated to the previous dose at the discretion of the physician.	
	Congestive heart failure or myocardial ischemia	Withhold carfilzomib until resolved or returned to baseline. Restart at the dose used prior to the event or reduced dose (from 27 mg/m ² to 20 mg/m ² , OR from 20 mg/m ² to 15 mg/m ²), at the discretion of the physician. If tolerated, the reduced dose may be escalated to the previous dose at the discretion of the physician.	
	Rash, or hand-foot syndrome only		Withhold cabozantinib until recovery to Grade 1 or screening value. Administer cabozantinib at the next lower dose for subsequent cycles, unless further dose reduction is required. If a second hold is required for the same event, administer cabozantinib at lower dose for subsequent cycles.

Event Grade (NCI CTC V4.03) and Category		Action by Agent	
Grade	Adverse Event	Carfilzomib	Cabozantinib
	Non-hematologic toxicities		Continue current dose level.
Grade 3	Hematologic (neutropenia, thrombocytopenia, anemia)	
Withhold carfilzomib dose.
 
If fully recovered before next scheduled dose, continue at same dose level.
 
If recovered to Grade 2 neutropenia or Grade 3 thrombocytopenia, reduce dose by one dose level: from 27 mg/m² to 20 mg/m², OR from 20 mg/m² to 15 mg/m².
 
If tolerated, the reduced dose may be escalated to the previous dose at the discretion of the physician.
 
TMA: If TMA is suspected, hold carfilzomib and manage per standard of care. If TMA is confirmed and related to carfilzomib, permanently discontinue carfilzomib. If TMA is excluded, may restart carfilzomib.
	
Withhold cabozantinib.
 
If the relevant lab value recovers to: $1.0 \times 10^9/L$ for ANC, 8 g/dL for hemoglobin, or $50 \times 10^9/L$ for platelets, resume cabozantinib treatment at same dose level. If the relevant lab value takes more than 3 weeks to recover to the level described above, restart cabozantinib administration at the next lower dose. If a second hold is required for the same event, administer cabozantinib at the next lower dose for subsequent cycles (for those subjects starting at 40 mg dose, cabozantinib would be discontinued if second hold required).

	Hepatic Toxicity	
25% dose reduction in case of baseline or treatment emergent mild or moderate hepatic impairment. Withhold carfilzomib until resolved or returned to baseline. After resolution, consider if restarting is appropriate. May be restarted at the dose (from 27 mg/m² to 20 mg/m², OR from 20 mg/m² to 15 mg/m²) with frequent monitoring of liver function. If tolerated, the reduced dose may be escalated to the previous dose at the discretion of the physician. Monitor liver enzymes regularly, regardless of baseline values, and modify dose based on toxicity.
	

Event Grade (NCI CTC V4.03) and Category		Action by Agent	
Grade	Adverse Event	Carfilzomib	Cabozantinib
	Renal	Serum creatinine ≥ 2 times baseline, CrCl < 15 mL/minute or CrCl decreases to $\leq 50\%$ of baseline, or patient requires dialysis: Withhold dose and monitor renal function. If renal toxicity is due to carfilzomib, resume dosing when renal function has improved to within 25% of baseline; resume with a reduced dose by 1 dose level.	
	Cardiac Toxicity: Grade 3 or 4, new onset or worsening of: 1. Congestive heart failure; 2. Decreased left ventricular function 3. Myocardial ischemia	Withhold until resolved or returned to baseline. After resolution, consider if restarting carfilzomib at a reduced dose is appropriate (from 27 mg/m ² to 20 mg/m ² , OR from 20 mg/m ² to 15 mg/m ²). If tolerated, the reduced dose may be escalated to the previous dose at the discretion of the physician.	
	Peripheral Neuropathy	Withhold until resolved or returned to baseline. After resolution, consider if restarting carfilzomib at a reduced dose is appropriate (from 27 mg/m ² to 20 mg/m ² , OR from 20 mg/m ² to 15 mg/m ²). If tolerated, the reduced dose may be escalated to the previous dose at the discretion of the physician.	
	Clinically significant Non-hematologic	Withhold until resolved or returned to baseline. After resolution, consider if restarting carfilzomib at a reduced dose is appropriate (from 27 mg/m ² to 20 mg/m ² , OR from 20 mg/m ² to 15 mg/m ²). If tolerated, the reduced dose may be escalated to the previous dose at the discretion of the physician.	Withhold cabozantinib until recovery to Grade 1 or screening value. Administer cabozantinib at the next lower dose for subsequent cycles, unless further dose reduction is required. If a second hold is required for the same event, administer cabozantinib at lower dose for subsequent cycles. For those subjects starting at 40 mg dose, cabozantinib would be

Event Grade (NCI CTC V4.03) and Category		Action by Agent	
Grade	Adverse Event	Carfilzomib	Cabozantinib
		PRES: If PRES is suspected, hold carfilzomib. Consider evaluating with MRI for onset of symptoms suggestive of PRES. If PRES if confirmed, permanently discontinue carfilzomib. If PRES is excluded, may resume carfilzomib at same dose if clinically appropriate.	discontinued if second hold required.
Grade 4	Non-hematologic (including hemorrhage and peripheral neuropathy)	Withhold carfilzomib until resolved or returned to baseline. Consider restarting at the next scheduled treatment with one dose level reduction (from 27 mg/m ² to 20 mg/m ² , OR from 20 mg/m ² to 15 mg/m ²). If tolerated, the reduced dose may be escalated to the previous dose at the discretion of the physician.	Withhold cabozantinib until recovery to Grade 1 or screening value. Consult with the Medical Monitor or designee prior to restarting cabozantinib. If the Investigator and Medical Monitor concur, administer cabozantinib at the next lower dose for subsequent cycles, unless further dose reduction is required. If a second hold is required for the same event, administer cabozantinib at lower dose for subsequent cycles. For those subjects starting at 40 mg dose, cabozantinib would be discontinued if second hold required.
	Hematologic (neutropenia, thrombocytopenia, anemia, febrile neutropenia)	Hold drug. If fully recovered before next scheduled dose, continue carfilzomib at same dose level. If recovered to Grade 2 neutropenia or Grade 3 thrombocytopenia, reduce dose by one dose level (from 27 mg/m ² to 20 mg/m ² , OR from 20 mg/m ² to 15 mg/m ²). If tolerated, the reduced dose may be escalated to the previous dose at the discretion of the physician.	Withhold cabozantinib. If the relevant lab value recovers to: 1.0×10 ⁹ /L for ANC, 8 g/dL for hemoglobin, or 50×10 ⁹ /L for platelets, resume treatment at next lower dose for subsequent cycles, unless further dose reduction is required.
Permanently discontinue for any of the following		1. Hypertensive crisis 2. Hypertensive emergency 3. Malignant hypertension	1. Development of visceral perforation or fistula formation 2. Severe hemorrhage 3. Serious arterial thromboembolic event (e.g., myocardial infarction, cerebral infarction) 4. Nephrotic syndrome

Event Grade (NCI CTC V4.03) and Category		Action by Agent	
Grade	Adverse Event	Carfilzomib	Cabozantinib
			
5. Malignant hypertension, hypertensive crisis, persistent uncontrolled hypertension despite optimal medical management
 
6. Osteonecrosis of the jaw
 
7. Reversible posterior leukoencephalopathy syndrome.

	Hepatitis B reactivation	Any subject who becomes HBV DNA positive or develops reactivation of HBV should have carfilzomib treatment interrupted and receive appropriate anti-viral treatment as per a specialist in Hepatitis B.	
	Progressive Multifocal Leukoencephalopathy (PML)	
Patients should be monitored for any new or worsening neurologic, cognitive or behavioral signs or symptoms that may be suggestive of PML as part of the differential diagnosis of CNS disorders.
 
If PML is suspected, patients should be promptly referred to a specialist and appropriate diagnostic testing should be initiated. Discontinue Kyprolis if PML diagnosis is confirmed.
	

Fatigue, Anorexia, and Weight Loss

Fatigue has been reported during treatment with cabozantinib. Common causes of fatigue such as anemia, deconditioning, emotional distress (depression and/or anxiety), poor nutrition, sleep disturbance, and hypothyroidism should be ruled out and/or these causes treated in accordance to standard of care. Individual non-pharmacological and/or pharmacologic interventions directed to the contributing and treatable factors should be given. Note: Chronic use of modafinil should be avoided because of its potential to reduce cabozantinib exposure (see Investigator's Brochure).

Anorexia and weight loss should be managed in accordance to local standard of care including nutritional support. If fatigue, anorexia, or weight loss cannot be adequately managed, study treatment should be temporarily interrupted or dose reduced per protocol.

Perforations and Fistulas:

Gastrointestinal (GI) perforations and fistulas were reported in 3% and 1% of cabozantinib treated patients, respectively. All were serious and one GI fistula was fatal (< 1%). Non-GI fistulas including tracheal/esophageal were reported in 4% of cabozantinib-treated patients. Two (1%) of these were fatal. **Cabozantinib should be discontinued in patients who experience a perforation or a fistula.**

Hemorrhage:

Serious and sometimes fatal hemorrhage occurred with cabozantinib. The incidence of Grade 3 hemorrhagic events was higher in cabozantinib-treated patients compared with placebo (3% vs. 1%). **Cabozantinib should be avoided in patients with a recent history of hemorrhage or hemoptysis.**

Thrombotic Events:

Cabozantinib treatment results in an increased incidence of thrombotic events (venous thromboembolism: 6% vs. 3% and arterial thromboembolism: 2% vs. 0% in cabozantinib-treated and placebo-treated patients, respectively). **Cabozantinib should be discontinued in patients who develop an acute myocardial infarction or any other clinically significant arterial thromboembolic complication.**

Subjects who develop a PE or DVT should have cabozantinib treatment held until therapeutic anticoagulation with heparins (eg, LMWH) is established. LMWH are the preferred management for thrombotic events, warfarin is not recommended. Cabozantinib treatment may be resumed in subjects who are stable and have uncomplicated PE or DVT and are deriving clinical benefit from cabozantinib treatment and that anticoagulation does not place them at a significant risk that outweighs the benefit of resuming treatment per discretion of the investigator/Sponsor.

Wound Complications:

Wound complications have been reported with cabozantinib. Treatment with cabozantinib should be stopped at least 28 days prior to scheduled surgery. Therapy can be resumed after surgery based on clinical judgment of adequate wound healing. **In patients with dehiscence or wound healing complications requiring medical intervention, therapy should be withheld.**

Hypertension:

Cabozantinib treatment results in an increased incidence of treatment-emergent hypertension with Joint National Committee on Prevention, Detection, Evaluation, and Treatment of High Blood Pressure (modified JNC criteria) stage 1 or 2 hypertension identified in 61% in cabozantinib-treated patients compared with 30% of placebo-treated patients in the randomized trial. Blood pressure should be monitored prior to initiation and regularly during cabozantinib treatment. It should be withheld for hypertension that is not adequately controlled with medical management; when controlled, cabozantinib can be resumed at a reduced dose. **It should be discontinued for severe hypertension that cannot be controlled with anti-hypertensive therapy.**

Osteonecrosis of the Jaw:

Osteonecrosis of the jaw (ONJ) occurred in 1% of cabozantinib-treated patients. ONJ can manifest as jaw pain, osteomyelitis, osteitis, bone erosion, tooth or periodontal infection,

toothache, gingival ulceration or erosion, persistent jaw pain or slow healing of the mouth or jaw after dental surgery. An oral examination should be performed prior to initiation of cabozantinib and periodically during cabozantinib therapy, and patients advised regarding good oral hygiene practices. For invasive dental procedures, cabozantinib should be withheld for at least 28 days prior to scheduled surgery, if possible.

Palmar-Plantar Erythrodysesthesia Syndrome:

Palmar-plantar erythrodysesthesia syndrome (PPES) occurred in 50% of patients treated with cabozantinib and was severe (Grade 3) in 13% of patients. Cabozantinib should be withheld in patients who develop intolerable Grade 2 PPES or Grade 3-4 PPES until improvement to Grade 1 when it can be resumed at a reduced dose.

Proteinuria:

Proteinuria was observed in 4 (2%) of patients receiving cabozantinib, including one with nephrotic syndrome, as compared to none of the patients receiving placebo. Urine protein should be monitored regularly during cabozantinib treatment and treatment **discontinued in patients who develop nephrotic syndrome.**

Reversible Posterior Leukoencephalopathy Syndrome:

Reversible Posterior Leukoencephalopathy Syndrome (RPLS), a syndrome of subcortical vasogenic edema diagnosed by characteristic finding on MRI, occurred in one (<1%) patient. An evaluation for RPLS should be performed in any patient presenting with seizures, headache, visual disturbances, confusion or altered mental function. **Discontinuation of cabozantinib should occur in patients who develop RPLS.**

Corrected QTc Prolongation

Cardiac arrest within 1 day of carfilzomib administration has been reported. If there is QT prolongation, we will consider holding carfilzomib.

If at any time on study there is an increase in QTcF to an absolute value > 500 ms or an increase of > 60 ms above baseline, two additional ECGs must be performed with intervals not less than 3 min apart within 30 min after the initial ECG.

If the average QTcF from the three ECGs is > 500 ms or increased by > 60 ms above baseline, the following actions must be taken:

- Interrupt study treatment
- Hospitalize symptomatic subjects (eg, with palpitations, dizziness, syncope, orthostatic hypotension, a significant ventricular arrhythmia on ECG) for a thorough cardiology evaluation and management
- Consider cardiology consultation for asymptomatic subjects for evaluation and management
- Check electrolytes, especially magnesium, potassium and calcium; correct abnormalities as clinically indicated
- Check concomitant medications for any medication that may have contributed to QT prolongation, and if possible, discontinue these medications (<http://www.qtdrugs.org>)
- Repeat ECG triplicates hourly until the average QTcF is ≤ 500 msec and the average increase is ≤ 60 ms above baseline, or otherwise determined by consultation with a cardiologist or appropriate expert.

